### **Secondary Outcomes:**

A main **secondary outcome** is change in PROMIS-ASF at 24 weeks. To evaluate Anxiety as a secondary outcome, we will conduct a difference-in-differences, Intent-To-Treat, repeated measures analysis using linear mixed effects models (mixed) to evaluate time  $\times$  intervention assignment interaction from baseline to 24 weeks, using a selected sample of participants with a baseline PROMIS-ASF  $> 16$  (T-score  $> 55$ ), which is the cutoff for mild anxiety disorder (since PROMIS-ASF is non-linear below this score). An additional **secondary outcome** is change in PROMIS-Pain Interference (PROMIS-PISF) at 24 weeks. Mixed effects models account for clustering of multiple observations within participants. We will compute contrasts of predictive margins to test for significant within-group changes and difference-in-differences (between-group) estimates over time. Between-group and within-group effect size (Cohen's  $d$ ) will be computed based on the predictive margins generated from the mixed models. To address missing data, we will implement multiple imputation methods in Stata (mi procedure). This technique creates multiple complete datasets, imputes missing values using a probabilistic simulation method (e.g., chained equations), analyzes each dataset, and uses standard rules to combine estimates and adjust standard errors for the uncertainty of imputation. Other **secondary clinical outcomes** include the number of positive oral fluid tests for BZD or cocaine during the final 12 weeks of the study.

For secondary and exploratory outcomes, we will use the Benjamini-Hochberg false discovery rate (FDR) procedure, which accounts for multiple comparisons. We will implement FDR according to Cao et al. in which a cutoff  $p$  value is determined for a family of similar variables and analyses (family-wise error rate = 0.05). Statistical significance will be determined for the following analysis families: between-group main secondary clinical outcomes (family size,  $n = 4$ ), and exploratory self-regulation outcomes ( $n=8$ ), exploratory other mechanistic outcomes ( $n=4$ ), exploratory clinical/health outcomes ( $n=15$ ), formal practices ( $n= 4$ ), informal practices ( $n = 7$ ), and resource use ( $n= 7$ ) (see section 9.5.2 for details).

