### 1.2 Secondary Objectives

**1.2.a. Clinical Co-morbidity:** Compare effects of M-ROCC vs. the control arm on anxiety and pain.

**H2a:** Among those with anxiety disorders, M-ROCC will have greater reduction in anxiety than control group at 24 weeks.

**H2b:** M-ROCC will have greater reduction in pain interference than control group at 24 weeks.

**1.2.b. Cocaine and Benzodiazepine Use:** Compare effects of live-online M-ROCC vs. the control arm on cocaine and benzodiazepine use.

**H3a:** M-ROCC will have fewer positive oral fluid tests for cocaine than a control group during weeks 13-24.

**H3b:** M-ROCC will have fewer positive oral fluid tests for BZDs than a control group during weeks 13-24.

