## **Screening Assessments (Consent and Screening Visit)**

After participant consent has been obtained, the research coordinator will provide the participant with a secure REDCap link to the PROMIS-ASF, and PhenX toolkit surveys, as well as a secure link to a screening CAT-MH survey, to evaluate for eligibility prior to proceeding with baseline assessments. The RC will also supervise an oral fluid test with the participant to assess for substance use. If the screening process suggests that the participant meets exclusion criteria or brings up other questions about eligibility, then the RC will contact the PI or clinical director to review the information and decide prior to proceeding to baseline assessments. If a participant's PROMIS-ASF T score is greater than 55 (Raw > 16), then the participant will be determined to have an anxiety disorder even if it was not previously diagnosed clinically.

Since participants with opioid use disorder often have transient mental health symptoms or intoxication related to recent substance use, participants with transient symptoms related to recent substance use may be able to wait for a re-review of eligibility after 30 days.

During this screening visit, all eligible participants will be asked to fill out a Scheduling Acceptability form to rate the level of acceptability of the available study group day and time for both M-ROCC and control group times at the site, asking on a 0-10 scale how much they will be able to attend the group times.

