Based on R21 urine toxicology data, we will focus our primary outcome analysis on the impact of M-ROCC on opioid use starting 12 weeks after intervention assignment. We estimate a mean of 4.67 negative tests for all illicit opioids (opiates, oxycodone, fentanyl, methadone) out of 6 random oral fluid toxicology tests conducted during the last 12 weeks in M-ROCC (SD 1.23) ( $n=78$ ) and 4.11 negative tests for all illicit opioids in the control check-in group (SD 1.27) ( $n=78$ ). We anticipate an effect size of Cohen's  $d = 0.45$  for between-group difference in percentage of monthly positive toxicology screens. Participation of  $N=192$  individuals randomized (with an effective sample size of 156 with 78 individuals in the M-ROCC arm and 78 individuals in the control group) allows for  $> 80\%$  power to detect an effect size of 0.45 for negative toxicology for all illicit opioids between M-ROCC and control arms. This power calculation was generated assuming a t-test of the difference between two means, a 1:1 intervention to control recruitment ratio, a type I error of 0.05, a two-sided comparison, and a design effect of 1.23 derived from an ICC of 0.01 with 8 group clusters with average cluster size of 24, which represents the average number of people randomized in each monthly cohort to either live-online M-ROCC or the live-online control group. This level of cluster was selected because it will encompass cohort effects. As the primary outcome will be analyzed in an intent-to-treat analysis, it is not sensitive to the number of individuals who drop out of the study after randomization. For secondary outcomes, based on pilot data and other relevant studies, we anticipate dropout from intervention in M-ROCC between 17-28% at 24-weeks and dropout in the control groups of 21-44% at 24-weeks.

In previous primary care studies, we have reported the impact of MTPC over 24 weeks on reductions in anxiety as measured by the PROMIS-ASF as  $d = -0.72$  ( $n=81$ ),  $p<0.001$  and  $d = -0.80$ ,  $p<0.001$  ( $n=136$ ). In our recent R21 pilot study, we reported significant Anxiety reductions over 24 weeks among patients with co-morbid anxiety at baseline ( $\geq 55$  at baseline) ( $p < .05$ ,  $ES = -0.556$ ). Given the

likelihood of a small effect of control on Anxiety after 4 weeks of buprenorphine treatment, we anticipate an effect size of  $d = -0.56$  for between-group change in PROMIS-ASF.

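### Anxiety and pain are compared by change from baseline without baseline adjustment, which costs some precision; within-arm anxiety tests also absorb regression to the mean

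*Combined protocol and SAP*

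**What the plan says.** **Model.** Section 9.6, Secondary Outcomes, specifies for anxiety a "difference-in-differences, Intent-To-Treat, repeated measures analysis using linear mixed effects models (mixed". The effect is the time by "intervention assignment interaction from baseline to 24 weeks, using a selected sample of participants with a baseline PROMIS-ASF" above a raw score of 16 (T above 55). Pain interference is named next as an additional secondary outcome. The mixed-model sentences that follow appear to cover both scales, but no subset is stated for pain. No baseline-score covariate and no equal-baseline constraint is given for either. The covariates mentioned elsewhere are scheduling acceptability (section 4.3) and, in the retention paragraph of section 9.6, a list to be added if the arms are imbalanced.

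**Within-arm results.** The same paragraph says: "We will compute contrasts of predictive margins to test for significant within-group changes and difference-in-differences (between-group) estimates over time". Within-group Cohen's d is planned as well.

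**Hypotheses.** Both are between-arm (section 1.2). The anxiety hypothesis, H2a, reads: "Among those with anxiety disorders, M-ROCC will have greater reduction in anxiety than control group at 24 weeks". The pain hypothesis, H2b, makes the corresponding between-arm claim and names no subset. The false discovery rate family for the four main secondary outcomes is also between-group.

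**Source of the anxiety baseline.** After consent, the coordinator is to "provide the participant with a secure REDCap link to the PROMIS-ASF". Tables 1a and 1b schedule PROMIS-ASF at screening and at weeks 8, 16 and 24, with no second measurement before randomisation.

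**Planning figure.** Section 9.2 reports from the R21 pilot "significant Anxiety reductions over 24 weeks among patients with co-morbid anxiety at baseline" (55 or above), with an effect size of -0.556. It then expects a small control effect and anticipates a between-group d of -0.56.

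**The concern.** Randomisation makes the expected baseline means equal. A difference-in-differences contrast does not use that fact: it estimates each arm's baseline mean separately and subtracts it, so baseline noise enters the treatment effect. Adjusting for baseline, or constraining the two means to be equal, gives the same estimand with a smaller standard error from data already collected.

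The second issue concerns anxiety only. People selected because one score exceeded 55 will on average score lower next time even if nothing has changed. That same score is their before value, so a significant fall within an arm is not evidence of benefit.

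The third is the planning figure. A between-arm effect is the M-ROCC change minus the control change. A one-arm change in a cutoff-selected group contains any control-type improvement and regression to the mean. At stake are the precision of two main secondary outcomes, the reading of within-arm results, and the realism of the anticipated anxiety effect.

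**Working it through.** **The plan's own figure.** The only power statement is for the primary outcome. Design effect = 1 + 23 × 0.01 = 1.23, and 192/1.23 = 156, or 78 per arm. The stated means and SDs (4.67 and 4.11; 1.23 and 1.27) give d = 0.448. With d = 0.45, 78 per arm and two-sided 0.05, power is 80.2% (normal approximation) or 79.7% (noncentral t), so the stated figure of over 80% reproduces to rounding. No power, SD, correlation or subset size is given for anxiety or pain. The inputs below are therefore assumptions, with complete data and no clustering.

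**Is it a change-score analysis?** In a simulated four-visit dataset, a mixed model with a free baseline gave an interaction of 0.491 at the last visit, identical to the simple difference in mean change.

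**Precision, pain (no selection).** Let r be the baseline to week-24 correlation, with equal variances at both times. The change-score variance is proportional to 2(1 - r) and the baseline-adjusted variance to 1 - r². Their ratio, adjusted over change, is (1 + r)/2.

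**Precision, anxiety (baseline above 55).** Let k be the share of baseline variance left after truncation. The adjusted variance is still proportional to 1 - r². The change-score variance is proportional to (1 - r²) + k(1 - r)². With screening mean 57 and SD 9 (assumed), the selected mean is 62.96 and k = 0.415.

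| r (unselected) | Variance cut, pain | Variance cut, anxiety subset |
|---|---|---|
| 0.4 | 30% | 15% |
| 0.5 | 25% | 12% |
| 0.6 | 20% | 9% |
| 0.7 | 15% | 7% |
| 0.8 | 10% | 4% |

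Simulated examples with SD 10 (assumed):

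- Pain, 78 per arm, 3.5-point effect: power rises from 58% to 69% at r = 0.5, and from 79% to 86% at r = 0.7.
- Anxiety subset, 47 per arm, 4.5-point effect, population mean 55: power rises from 66% to 70% at r = 0.5, and from 83% to 85% at r = 0.7.

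**Regression to the mean, anxiety subset.** Expected fall with no real change = (1 - r) × (62.96 - 57) = (1 - r) × 5.96.

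- r = 0.8: 1.2 T points
- r = 0.7: 1.8 T points
- r = 0.6: 2.4 T points

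The SD of the selected sample is 9 × √0.415 = 5.8, so these falls are 0.21, 0.31 and 0.41 SD. With SD 10, population means of 50-65 and r of 0.4-0.8, the range widens to 0.6-6.9 points.

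**What that does to the tests.** Simulations with no true change, 47 per arm and 2,000 runs per setting gave:

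| Test | Share significant |
|---|---|
| Within control arm, anxiety subset | 28% (mean 60, r 0.7) to 99% (mean 50, r 0.5) |
| Between arms, anxiety subset | 4.0-6.1% |

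The mean between-arm difference stayed within 0.1 point of zero. For unselected pain (78 per arm), the within-arm test rejected in about 5% of runs.

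**Planning figure.** Between-arm d = pilot change minus control change. If the control change is c on the same scale, d = -0.556 - c. For c = -0.1, -0.2 and -0.3 (assumed), d is -0.46, -0.36 and -0.26. Only c near zero returns -0.56.

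**The case against.** The strongest reply is that the planned inference is sound. A change-score contrast in a randomised trial is valid and unbiased, H2a and H2b are between-arm, and the main secondary multiplicity family holds between-group tests only. No within-arm test decides a hypothesis. All of this stands. A reader might infer that regression to the mean undermines the anxiety hypothesis test. It does not, because it acts equally in both arms and cancels.

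Two other stronger readings fail. One is that pain shares the selection problem; the cutoff is stated for PROMIS-ASF only. The other is that a saving of 25% or more applies to anxiety because selection lowers the correlation. The (1 + r)/2 formula needs equal variances at both times, and truncation breaks that; the saving becomes smaller, not larger.

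The sponsor can also say that a free baseline is not written out. True, but it is the natural reading of difference-in-differences with an interaction running from baseline, and no adjustment is stated. The reason section 9.6 gives for the cutoff, non-linearity of the scale below it, supports selecting the subset but does not remove the effect on within-arm results.

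On the planning figure, section 9.2 also cites changes of -0.72 and -0.80 from primary care studies, and the derivation of -0.56 is not given. It may be a judgement across sources. No sample size rests on it.

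**Conclusion.** The point holds as a free improvement, not as a flaw in the hypothesis tests. Baseline adjustment would reduce the variance of the between-arm contrast by about 10-30% for pain and about 4-15% for anxiety, over unselected correlations of 0.4-0.8; the anxiety range also assumes screening mean 57 and SD 9. Within-arm tests and within-arm d for anxiety cannot separate real change from regression to the mean. Its size is about 1.2-2.4 T points at correlations of 0.6-0.8 under the same mean and SD, and wider under other assumptions.

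The anticipated anxiety d shows no visible subtraction of the control effect that the same sentence expects. One might infer that the true value is -0.26 to -0.36, or that the trial is underpowered for anxiety. The documents support neither: that range rests on an assumed control change of -0.2 to -0.3, and they give no anxiety power or subset size.

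**What to change.** 1. In section 9.6, keep the mixed model but fit it with one baseline mean common to both arms, or use the baseline score as covariate with weeks 8, 16 and 24 as outcomes. Apply this to PROMIS-ASF and PROMIS-PISF. Apply it also to the eight self-regulation scales and the ten exploratory clinical scales whose analysis refers back to the same models, using each scale's own follow-up visits.
2. Name the week-24 between-arm contrast as the test.
3. Report within-arm changes with estimates and intervals but no p-values, and note that for anxiety they include regression to the mean.
4. In section 9.2, restate the anticipated anxiety d as M-ROCC change minus control change, and give the control change assumed.

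The cost is SAP wording. Data, visits and software stay the same. If adjustment was always intended, item 1 only records it. The one real price is that the anticipated anxiety effect becomes less favourable.

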#### **9.2 Sample Size and Randomization**

##### Justification of Sample Size and Power Calculations:

This study will enroll an approximate of  $n = 236$  and maximum of  $n = 280$  participants who will sign informed consent and our power analyses have identified that we will have the sample to identify meaningful effects with an effective sample size of  $n=156$  with 78 individuals in the M-ROCC arm and 78 individuals in the control group. We expect to randomize at least 192 participants (96 M-ROCC: 96 Control) over 8 months in order to have an effective sample size of  $n=156$ . We will aim to recruit participants with an active buprenorphine prescription from providers in U.S. states approved for recruitment by the IRB to enroll patients at a rate of approximately 30 participants per month, anticipating 19% loss during screening and baseline assessments, so we can randomize approximately 24 participants each month for 8 months.

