### **Oral Fluid Toxicology Testing**:

The minimally invasive nature of sample collection is a key advantage of oral fluid over traditional biospecimens. An IDE is not required for these saliva tests because they are non-invasive and are not being evaluated to determine safety or effectiveness. The two dominant methods are collection of whole saliva by passive drool and collection of saliva by absorbent material placed in the mouth. A sponge method of collection will be used for oral fluid toxicology testing. Oral fluid toxicology testing will be supervised via videochat with a study staff member to ensure that there is no tampering with the collection.

Preparation: All subjects will be sent a package after enrollment and initial screening with sponge-based oral fluid toxicology testing kits. Tests will be sent at screening to

participants' homes to be taken at randomly selected time points during the intervention or control group (at least 9 samples will be collected for each participant with at least 6 between weeks 13-24).

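### The cocaine and benzodiazepine outcomes are numbers of positive tests with no denominator and no rule for untaken tests; read literally, the arm with more missing tests looks better

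*Combined protocol and SAP*

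**What the plan says.** Section 9.6 (Secondary Outcomes) gives these two outcomes one sentence, which describes them as "the number of positive oral fluid tests for BZD or cocaine during the final 12 weeks of the study". The Précis uses the same wording. Section 9.5.2 lists cocaine and benzodiazepines separately, as positive tests in weeks 13-24. Hypothesis H3a in Section 1.2 reads "M-ROCC will have fewer positive oral fluid tests for cocaine than a control group during weeks 13-24", and H3b says the same for benzodiazepines. Together they are two of the four outcomes in the main secondary family for the false discovery rate procedure.

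On the number of tests, Section 10.1 says "at least 9 samples will be collected for each participant with at least 6 between weeks 13-24". On loss, Section 9.2 anticipates "dropout from intervention in M-ROCC between 17-28% at 24-weeks and dropout in the control groups of 21-44% at 24-weeks".

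The methods nearby are these:

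- The Primary Outcome part of Section 9.6 specifies GEE over six two-week periods, with a binomial distribution and logit link for dichotomous outcomes, and multiple imputation.
- The Secondary Outcomes part specifies linear mixed models for the PROMIS scales, then multiple imputation, and then comes the toxicology sentence.
- Section 5.1 expects a participant who misses group when selected for testing to be tested by video within 24 hours.
- Section 8 generally expects participants who stop the group to complete outcome assessments unless they withdraw consent.

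**The concern.** A test that is not taken adds nothing to a count of positives. If the outcome is each participant's total, a participant with two tests, both negative, scores zero, exactly like one with six negatives. The primary outcome does not share this property: a period counts as abstinent only with a negative test, so a missing test earns no credit by definition.

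Imputation does not repair this automatically. It fills values that are coded missing, and a participant with two of six tests still has a computable number of positives. Unless each scheduled test is the unit of analysis, nothing is flagged for imputation.

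Routine testing takes place in the group check-in, so leaving the group removes the usual testing occasion. If more control than M-ROCC participants leave, control may show fewer positives with no difference in use. H3a and H3b could then be missed or appear reversed.

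**Working it through.** **The plan's own figure.** The only stated power is for the primary outcome (above 80%). The M-ROCC input is "We estimate a mean of 4.67 negative tests for all illicit opioids" (SD 1.23) and the control input is 4.11 (SD 1.27). Then d = (4.67 − 4.11)/√((1.23² + 1.27²)/2) = 0.448, which the plan rounds to 0.45. The plan uses "a type I error of 0.05, a two-sided comparison, and a design effect of 1.23 derived from an ICC of 0.01": 1 + (24 − 1) × 0.01 = 1.23, and 192/1.23 = 156.1, or 78 per arm. Power is 80.2% by the normal approximation and 79.7% by the t-test version. The figure reproduces and this point does not affect it. No power or error rate is stated for cocaine or benzodiazepines.

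**Inputs for the check.** From the plan:

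- 96 per arm ("We expect to randomize at least 192 participants (96 M-ROCC: 96 Control) over 8 months")
- six tests in the window
- two-sided 0.05
- the dropout ranges in Section 9.2, with midpoints (17 + 28)/2 = 22.5% and (21 + 44)/2 = 32.5%.

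Assumed, because the plan gives neither: positivity p = 0.20 per test in both arms (the null) and within-person correlation ρ = 0.5. Also assumed: dropouts miss all six tests or half of them, missing tests are unrelated to use, and untaken tests count as not positive.

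**Formulas.** Let r be the fraction of an arm that is fully tested.

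- Six tests: mean 6p = 1.2; variance 6p(1 − p)(1 + 5ρ) = 0.96 × 3.5 = 3.36.
- Dropouts miss all six: arm mean 1.2r; variance 3.36r + 1.44r(1 − r).
- Dropouts take three: their mean is 0.6 and variance 3 × 0.16 × (1 + 2ρ) = 0.96. Arm mean 1.2r + 0.6(1 − r); variance 3.36r + 0.96(1 − r) + 0.36r(1 − r).
- z = difference in means / √((V₁ + V₂)/96); rejection = P(Z > 1.96 − z) + P(Z < −1.96 − z).

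**Example: 17% v 44%, all six missed.** Means are 1.2 × 0.83 = 0.996 and 1.2 × 0.56 = 0.672. Variances are 2.992 and 2.236. SE = √(5.228/96) = 0.233 and z = 0.324/0.233 = 1.39. Rejection = 28.38% + 0.04% = 28.4%; a simulation of 3,000 trials gave 28.9%.

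| Dropout, M-ROCC v control | Tests missed by dropouts | Mean count, M-ROCC v control | Lower count | Type I error |
|---|---|---|---|---|
| 17% v 44% | all six | 0.996 v 0.672 | control, by 33% | 28.4% |
| 17% v 44% | half | 1.098 v 0.936 | control, by 15% | 10.5% |
| 22.5% v 32.5% | all six | 0.930 v 0.810 | control, by 13% | 8.0% |
| 22.5% v 32.5% | half | 1.065 v 1.005 | control, by 6% | 5.7% |
| 28% v 21% | all six | 0.864 v 0.948 | M-ROCC, by 9% | 6.4% |

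**Direction.** In the first row nearly all false rejections favour control (28.38% against 0.04%). In the last row, 5.3 of the 6.4 percentage points favour M-ROCC, against a nominal 2.5.

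**Masking.** The percentages in the fourth column depend only on the fraction of tests taken, not on p or ρ. In the first row, positivity under M-ROCC would have to be 33% lower than in control (1 − 0.56/0.83) merely to produce equal counts.

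**Sensitivity to the assumed inputs.** Over p = 0.05-0.40 and ρ = 0.3-0.7:

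- 17% v 44%, all tests missed: 9-66%
- 17% v 44%, half missed: 6-25%
- midpoints, all missed: 5.5-14%.

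With 78 effective per arm instead of 96, the 28.4% becomes 24%. At the strictest Benjamini-Hochberg step for four tests (0.05/4 = 0.0125) it becomes about 13%.

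**With a denominator.** Testing the proportion of completed tests that are positive, or positives over tests taken with clustered standard errors, gives simulated type I error of about 4-7% in every scenario, including 17% v 44%. This holds when missing tests are unrelated to use.

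**The case against.** The best defence is that the plan never says an untaken test is non-positive. It also describes the primary outcome as a number of periods, yet analyses it period by period with GEE and imputation, so a number need not mean a raw total. Imputation is stated under Secondary Outcomes immediately before the toxicology sentence, and the clause on dichotomous outcomes could be read as general. This stands in part. It would be wrong to infer that the plan has no missing-data method for secondary outcomes, or that imputation is confined to the PROMIS scales. What remains is that neither method is attached to these two outcomes, and that imputation has nothing to act on if the unit is a person's total.

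The second defence is that the dropout figures concern the intervention, not the tests. Section 8 generally expects assessments to continue, Section 5.1 provides a make-up test, and completed testing is paid for. Dropout is also cumulative to week 24, so a participant who leaves late has already had test opportunities in the window. This stands. These provisions reduce the loss but cannot guarantee tests, which is why the half-missed scenarios are shown.

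A reader might infer that the plan's dropout range by itself lifts type I error to 28%. The documents do not support that. The figure pairs the lowest M-ROCC dropout with the highest control dropout, treats every dropout as losing all six tests, and uses a positivity and a correlation that the plan does not give. Nor do the figures point mainly to a false claim of benefit for M-ROCC; across most of the stated ranges the error favours control.

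**Conclusion.** The gap is real: two of the four main secondary outcomes have no stated model, denominator or rule for untaken tests, and the literal wording credits an untaken test as a negative. How much this matters depends on how many tests are lost in each arm, which the plan does not forecast. Under the stated assumptions the inflation is small at the dropout midpoints (about 6-8%), moderate at 17% v 44% with half the tests missed (about 11%), and large (about 28%) only in the worst corner. The likelier harm is a real benefit on H3a or H3b that is hidden or reversed. The primary analysis and its power are unaffected. The point should be settled before analysis, so that the choice between a count and a per-test model is not made with the data in view.

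**What to change.** In Sections 9.5.2 and 9.6, define for each participant and each of the six two-week periods in weeks 13-24 a result of positive, negative or missing, separately for cocaine and for benzodiazepines. State that an untaken test is missing. Analyse the six periods with the binomial-logit GEE and multiple imputation already named for the primary outcome, imputing at the level of the period. Report the odds ratio and the proportion positive by arm, together with the number of tests taken by arm.

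Add a sensitivity analysis for missingness related to use, for example by making imputed tests progressively more likely to be positive than observed ones. The GEE with imputation removes the mechanical credit for untaken tests, but not bias that arises when people who are using avoid testing.

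The cost is SAP wording and slightly more analysis work, with the same data and software. The effect is reported as an odds ratio or proportion instead of a count. The family of four outcomes is unchanged.

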### 9.5.2 Secondary Outcomes

#### Main Secondary Clinical Outcomes:

1. Patient Report Outcomes Measurement Information System – Anxiety Short Form 8a (PROMIS-ASF)
2. Patient Report Outcomes Measurement Information System – Pain Interference Scale (PROMIS-PISF)
3. Positive oral fluid toxicology tests for Cocaine during the final 12 weeks (weeks 13-24) of the study.
4. Positive oral fluid toxicology tests for Benzodiazepines during the final 12 weeks (weeks 13-24) of the study.

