#### Exploratory Self-regulation mechanistic outcomes

1. Brief Experiential Avoidance Questionnaire (BEAQ) (EMO)
2. Difficulties in Emotion Regulation Scale (DERS-16) (EMO)
3. Perceived Stress Scale (PSS) (EMO)
4. Self-Compassion Scale (SCS) (SRP)
5. Multidimensional Assessment of Interoceptive Awareness subscales 1, 4-8 (MAIA) (SRP)
6. Nonattachment to Self Scale (NTS) (SRP)
7. Self-Critical Rumination Scale (SCRS) (SRP)
8. Experiences Questionnaire- Decentering Subscale (COG/EMO)

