#### Exploratory Other Mechanistic outcomes:

1. Five Facet Mindfulness Questionnaire (FFMQ)
2. Interpersonal Mindfulness Scale (IMS)
3. Group Cohesion Questionnaire (GCQ)
4. M-ROCC Qualitative Interviews
5. Credibility/Expectancy Survey (OUD)
6. Credibility/Expectancy Survey (Stress)

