#### Exploratory Clinical Outcomes:

1. Intervention retention at 24 weeks, defined as any **active BUP prescription** within the last 28 days (i.e., between Weeks 20-24 of participant enrollment).
2. Time to intervention discontinuation

3. Weekly Survey reports of BUP non-adherence [a] and diversion [b]
4. Medication-assisted treatment status at 24 weeks (including methadone, buprenorphine or naltrexone).
5. Self-reported average daily dose of BZDs prescribed over final 12 weeks
6. Beck Anxiety Inventory (BAI)
7. Pain Catastrophizing Scale (PCS)
8. Substance Craving Scale (SUBCS)

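### Benjamini-Hochberg is given a family-wise error rate of 0.05 that it does not guarantee, and the size of the other-mechanistic family does not match its list

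*Combined protocol and SAP*

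**What the plan says.** In the combined protocol and SAP, section 9.6 (Secondary Outcomes) states for secondary and exploratory outcomes: "we will use the Benjamini-Hochberg false discovery rate (FDR) procedure". It then says that a cut-off p-value is determined "for a family of similar variables and analyses (family-wise error rate = 0.05").

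The same paragraph gives the family sizes: 4 for "between-group main secondary clinical outcomes", 8 for self-regulation, 4 for "exploratory other mechanistic outcomes", 15 for clinical/health outcomes, and 4, 7 and 7 for formal practices, informal practices and resource use. It refers to section 9.5.2 for details.

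Section 9.5.2 lists:

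- four main secondary outcomes, ending with "4. Positive oral fluid toxicology tests for Benzodiazepines during the final 12 weeks (weeks 13-24) of the study";
- eight self-regulation outcomes, ending with "8. Experiences Questionnaire- Decentering Subscale (COG/EMO");
- six other mechanistic outcomes, beginning with "Five Facet Mindfulness Questionnaire (FFMQ") and including the qualitative interviews and two Credibility/Expectancy surveys (OUD and Stress);
- fifteen numbered clinical outcomes, the third being "Weekly Survey reports of BUP non-adherence [a] and diversion [b"].

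**The concern.** The false discovery rate is the expected share of false claims among all claims made. The family-wise rate is the chance of making any false claim. The plan names a procedure for the first and attaches a level for the second. The two coincide when every null in the family is true. Section 1.2, however, hypothesises an effect on all four main secondary outcomes (H2a, H2b, H3a, H3b), so the plan expects to be in the situation where they part.

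Two things are at stake. A reader of the anxiety, pain, cocaine and benzodiazepine results could take the chance of any false claim to be capped at 5%. An analyst could also read the sentence as asking for a method that does control the family-wise rate, and that method can give different significance calls on the same p-values.

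Family size matters because the cut-offs depend on it: the i-th smallest p-value is compared with i × 0.05/m. If m is smaller than the number of tests, every cut-off is too lenient.

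**Working it through.** **Inputs.** Procedure, level 0.05 and family sizes come from section 9.6; the lists come from section 9.5.2. Write m for the family size and m0 for the number of true nulls.

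**1. The plan's figure.** With m = 4, independent tests and all four nulls true, the Benjamini-Hochberg family-wise rate is exactly 0.05. The stated figure reproduces in that case.

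**2. Worst case for m = 4.** Take independent tests and let the false nulls always be rejected. The cut-offs are 0.0125, 0.025, 0.0375 and 0.05.

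- *m0 = 2.* The sure rejections use the first two cut-offs. A true null is rejected if the smaller of the two null p-values is at most 0.0375, or if both lie between 0.0375 and 0.05: 1 − (1 − 0.0375)² + (0.05 − 0.0375)² = 1 − 0.92641 + 0.00016 = 0.0737.
- *m0 = 3.* The remaining cut-offs are 0.025, 0.0375 and 0.05. The same reasoning gives 1 − 0.975³ = 0.07314; plus 3 × 0.0125² × 0.9625 + 0.0125³ = 0.00045; plus 4 × 0.0125³ = 0.00001. The total is 0.0736.
- *m0 = 1.* The rate is 0.05.

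The maximum is therefore 7.4%. Simulation with 2,000,000 replicates per case gave 0.0732 (m0 = 2) and 0.0738 (m0 = 3).

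**3. Less extreme cases for m = 4.** Here each real effect has 80% power at an unadjusted 0.05.

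| Correlation between tests | m0 = 3 | m0 = 2 |
|---|---|---|
| 0 | 6.4% | 6.2% |
| 0.5 | 5.5% | 5.3% |

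**4. Larger families.** The same exact calculation gives a maximum of 0.1195 for m = 8 (at m0 = 4) and 0.1947 for m = 15 (at m0 = 8).

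**5. With the label corrected.** Under independence the false discovery rate is (m0/4) × 0.05, which is at most 0.05. The procedure does deliver 0.05 on that scale.

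**6. Why the reading matters.** For four outcomes, Holm uses 0.05/4, 0.05/3, 0.05/2 and 0.05/1, that is 0.0125, 0.0167, 0.025 and 0.05. A second-smallest p-value between 0.0167 and 0.025 is significant under Benjamini-Hochberg and not under Holm.

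**7. Family sizes against section 9.5.2.**

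| Family | Stated | Listed |
|---|---|---|
| Main secondary | 4 | 4 |
| Self-regulation | 8 | 8 |
| Other mechanistic | 4 | 6 (5 without the interviews) |
| Clinical | 15 | 15 numbered |

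If five p-values are compared with i × 0.05/4, this equals i × q/5 with q = 0.05 × 5/4 = 0.0625.

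**The case against.** The strongest reply is that nothing in the main analysis changes. The plan names the false discovery rate twice around the faulty parenthesis. The procedure and the 0.05 level are clear, and correcting the label alters no cut-off. The main secondary family size is right, and false discovery control is a legitimate choice for secondary outcomes. All of this stands. It limits the consequence, but the plan still claims an error rate that its procedure does not guarantee.

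On the other-mechanistic family, 4 can be reached by dropping the interviews, which yield no p-value, and counting expectancy once. The Exploratory analyses text in section 9.6 does refer to a single Credibility/Expectancy Survey. Against this, section 9.5.2 lists the two surveys separately, Table 1a gives them separate rows, and section 10.1 describes two six-item instruments. The plan nowhere says that they are merged. What stands is that 5 is not established either: both surveys are given only at week 2, and section 9.6 treats some of these variables as possible covariates or mediators.

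Two stronger readings are tempting, and the documents do not support them:

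- A reader might infer that the family-wise rate for the main secondary outcomes simply is about 7.5%. That figure is the union bound (2 × 0.0375 or 3 × 0.025) on a worst case whose exact value is 7.4%. The rate is lower in the 80%-power scenarios above and is 5% under the complete null.
- A reader might infer that the clinical family should be 16. The stated 15 agrees with the numbered list. Sixteen requires the two parts of item 3 to be separate tests, which the plan does not say.

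**Conclusion.** The point holds in two parts. First, the error rate is mislabelled. The family-wise rate is 0.05 under the complete null but can reach 7.4% for the four main secondary outcomes, and about 12% and 19.5% for families of 8 and 15. These maxima assume independent tests and certain rejection of every real effect; the 7.4% also needs two or three of the four nulls to be true. With 80% power the excess for the main secondary family is smaller, at 5.3% to 6.4% in the scenarios examined.

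Second, the other-mechanistic size of 4 does not agree with the six listed items, five of them quantitative. The 0.0625 bound applies only if five p-values are tested against cut-offs for four, and it concerns one exploratory family.

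The correction is worth making because the plan should state the error rate it delivers and allow only one reading.

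**What to change.** In section 9.6:

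1. Replace the family-wise statement with a false discovery rate of q = 0.05 for all families. If family-wise control is truly intended for the four main secondary outcomes, name Holm or Hochberg for that family only.
2. Set m for the other-mechanistic family to the number of between-group tests actually run (5 if both Credibility/Expectancy surveys are tested) and reconcile it with section 9.5.2.
3. Keep 15 for the clinical family unless non-adherence and diversion are tested separately, and state whether they are one test or two.
4. In the same edit, list the members of the formal-practice, informal-practice and resource-use families. The text sends the reader to section 9.5.2 for them, but they are not there.

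The cost is a wording change before database lock, with no new data. Choosing Holm would make the second and third cut-offs for the main secondary outcomes stricter (0.0167 and 0.025 in place of 0.025 and 0.0375).
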